[figure not shown]
UPR Unanticipated Problems involving Risk to subjects or others
WBC White Blood Cells

STUDY SCHEMA

Cycle 1

Cycle 2-5

STUDY SUMMARY

Title	A Phase I/II study of blinatumomab in combination with pembrolizumab (MK-3475) for adults with relapsed or refractory B-lineage acute lymphoblastic leukemia (ALL) with high bone marrow lymphoblast percentage: University of California Hematologic Malignancies Consortium study #1504 (UCHMC1504)
Short Title	Phase I/II study of blinatumomab with pembrolizumab for adults with relapsed or refractory B-lineage acute lymphoblastic leukemia
Phase	I/II
Methodology	Phase I/II of blinatumomab in combination with pembrolizumab in adult patients with relapsed or refractory B-lineage ALL

Study Duration	48 months
Study Center(s)	Multi-center: UCSD, UCD, UCI,UCSF
Objectives	
Primary:
 
To determine if the addition of pembrolizumab to blinatumomab improves the overall response rate (CR+ CRh) relative to blinatumomab alone in adult subjects with relapsed or refractory B-cell acute lymphoblastic leukemia with high bone marrow lymphoblast percentage
 
Secondary:
 
To estimate CR rate
 
To estimate the minimal residual disease (MRD) negativity rate in subjects achieving a CR or CRh
 
To estimate 2-year relapse-free survival (RFS)
 
To estimate 2-year overall survival (OS)
 
To estimate ORR, CR, CRh, 2-year RFS, and 2-year OS in the Ph/BCR-ABL1-negative and Ph/BCR-ABL1–positive populations separately
 
To determine the allogeneic hematopoietic cell transplantation rate in transplant-eligible subjects
 
To determine the safety and tolerability of blinatumomab in combination with pembrolizumab
 
Exploratory:
 
To determine PD-1 expression on T-cells and PD-L1 and PD-L2 protein expression on lymphoblasts at diagnosis and in response to therapy
 
To determine changes in bone marrow and peripheral blood T-cell populations in response to therapy with blinatumomab and the combination of blinatumomab and pembrolizumab.
 
To determine changes in PD-1, PD-L1 and PD-L2 expression with blinatumomab exposure and correlation with disease response
 
To determine changes in cytokine response with therapy and correlate with PD-1, PD-L1 and PD-L2 expression changes

Number of Subjects	24


Diagnosis and Main Inclusion Criteria
	
Inclusion
 
 1. Relapsed or refractory CD19-positive B-lineage acute lymphoblastic leukemia having received at least 1 prior line of therapy 2. Philadelphia chromosome/BCR-ABL1-positive B-lineage ALL must have failed at least 1 second or third generation tyrosine kinase inhibitor (TKI) or be intolerant to TKIs 3. Greater than 50% lymphoblasts on screening bone marrow aspirate or biopsy 4. Evidence of CD19 expression via flow cytometry (peripheral blood or bone marrow) or immunohistochemistry (bone marrow biopsy) from a sample obtained from the current relapse 5. Adults 18 years of age or older 6. ECOG performance status of 0 or 1 7. Adequate organ function defined as: 
 - Bilirubin <1.5x upper limit of normal (ULN) unless believed due to leukemic infiltration - AST or ALT \leq2.5x ULN unless believed due to leukemic infiltration - creatinine clearance >60 mL/min/1.73 m² unless reduced creatinine clearance felt by investigator to be acute and reversible 8. Ability to understand and the willingness to sign a written informed consent. 9. Women of child-bearing potential and men with partners of child-bearing potential must agree to use 2 methods of birth control or be surgically sterile, or abstain from heterosexual activity for the course of the study through 120 days after the last dose of study medication. Should a woman become pregnant or suspect she is pregnant while participating in this study, she should inform her treating physician immediately. 
 a. A woman of child-bearing potential is any female (regardless of sexual orientation, having undergone a tubal ligation, or remaining celibate by choice) who meets the following criteria: 
 i. Has not undergone a hysterectomy or bilateral oophorectomy; or ii. Has not been naturally postmenopausal for at least 12 consecutive months (i.e., has had menses at any time in the preceding 12 consecutive months) 10. Women of child-bearing potential has negative pregnancy test within 72 hours of initiating study drug dosing.
--	--

	
11. Male subjects must agree to use a latex condom during sexual contact with females of childbearing potential even if they had a successful vasectomy starting with the first dose of study therapy through 120 days after the last dose of study therapy.
 
12. Corticosteroids and hydroxyurea are permitted after screening bone marrow biopsy is performed and for up to 7 days prior to starting study therapy
 
Exclusion
 
 1. Allogeneic HSCT within 5 years of study drug administration 2. Is currently participating and receiving study therapy or has participated in a study of an investigational agent and received study therapy or used an investigational device within 4 weeks of the first dose of treatment. 3. GM-CSF or G-CSF use within 2 weeks of study treatment and throughout the study. 4. Prior checkpoint inhibitor therapy including anti-PD1, anti-PD-L1, anti-CTLA4, anti- CD137, or anti-PD-L2 therapy 5. Prior treatment with any CD19-directed therapy (e.g. blinatumomab, CD19-directed chimeric antigen receptor T-cell therapy, anti-CD19 antibodies). 6. Clinical evidence of active CNS involvement by leukemia 7. History of neurologic disorder including but not limited to: prior seizure, epilepsy, structural brain abnormality, benign brain tumor, stroke, brain injuries, dementia, movement disorder or other significant CNS abnormalities. 8. Has a known additional malignancy that is progressing or requires active treatment. Exceptions include basal cell carcinoma of the skin, squamous cell carcinoma of the skin, or in situ cervical cancer that has undergone potentially curative therapy. 9. Burkitt lymphoma/leukemia 10. Has a diagnosis of congenital immunodeficiency 11. Has a known history of active TB (Bacillus Tuberculosis) 12. Known HIV infection 13. Active hepatitis B or hepatitis C infection 14. Any uncontrolled infection 15. Has received a live vaccine within 30 days prior to first dose 16. Is pregnant or breastfeeding, or expecting to conceive or father children within the projected duration of the trial, starting with the pre-screening or screening visit through 120 days after the last dose of trial treatment. 17. Non-pregnant, non-breast-feeding women may be
--	--

	
enrolled if they are willing to use 2 methods of birth control or are considered highly unlikely to conceive. Highly unlikely to conceive is defined as 1) surgically sterilized, or 2) postmenopausal (a woman who is ≥ 45 years of age and has not had menses for greater than 1 year will be considered postmenopausal), or 3) not heterosexually active for the duration of the study. The two birth control methods can be either two barrier methods or a barrier method plus a hormonal method to prevent pregnancy. Subjects should start using birth control from study Day 1 throughout the study period up to 120 days after the last dose of study therapy.
 
 18. History of autoimmune disease 19. Known interstitial lung disease 20. Any evidence of active, non-infectious pneumonitis or has a history of (non-infectious) pneumonitis that required steroids or current pneumonitis 21. Patients who have received chemotherapy or radiotherapy within 4 weeks prior to entering the study or has not recovered from adverse events due to agents administered more than 4 weeks earlier. 22. Patients who are less than 4 weeks from surgery or have insufficient recovery from surgical-related trauma or wound healing. 23. History of allergic reactions attributed to compounds of similar chemical or biologic composition to blinatumomab or pembrolizumab or other agents used in study. 24. Known impaired cardiac function including any of the following: 
 a) History or presence of clinically significant ventricular or atrial tachyarrhythmias; b) Clinically significant resting bradycardia (< 50 beats per minute); c) Myocardial infarction within 1 year of starting study drug; d) Other clinically significant heart disease (e.g., unstable angina, uncontrolled congestive heart failure, or uncontrolled hypertension). 25. Any condition that requires the use of corticosteroids after Day 1 of therapy with the exception of topical or inhaled steroids. Prednisone dose or equivalent of 5mg/day is allowed. 26. Severe or uncontrolled medical disorder that would, in the investigator's opinion, impair ability to receive study treatment (i.e., uncontrolled diabetes, chronic renal disease, chronic pulmonary disease or active, uncontrolled infection, psychiatric illness/social situations that would limit compliance with study
--	---

	requirements)
Study Product(s), Dose, Route, Regimen	Blinatumomab Pembrolizumab
Duration of administration	28 weeks
Reference therapy	Blinatumomab alone, historical (Topp et al. 2015)
Statistical Methodology	One-sided binomial, Kaplan Meier estimates, chi-squared

Period/ Procedure	Screening	Treatment (42 day cycles)															End of Treatment	Follow up	Relapse	
		Cycle 1							Cycle 2				Cycle 3-5							
Day	-21 to -1	1	8	14	15	28	29 +8	36	1	15	29 +8	36	1	15	29 +8 ^m	36	Day 38 +8 days of Cycle 5	Every 3 Mos		
Informed Consent	X																			
Treatment																				
Pembrolizumab					X			X		X		X		X		X				
Blinatumomab		X ^a			X ^b					X ^b				X ^b						
Methotrexate	X ^c						X ^c				X ^c				X ^{c,m}		X			
Clinical Procedures																				
Review of Eligibility Criteria	X																			
Demographics	X																			
Medical History	X																			
Performance Status (ECOG)	X	X							X					X			X			
Vital Signs, Weight ^d	X	X							X					X			X	X	X	
Height	X																			
Physical Exam ^e	X	X							X					X			X	X	X	
PET/CT Scan (if palpable lymphadenopathy and/or evidence of extramedullary masses) ^f	X																X			X
CT Scan (if palpable lymphadenopathy and/or evidence of extramedullary masses) ^f							X				X									
Bone Marrow Aspiration/ Biopsy ^g	X			X			X				X					X ^m	X			X

Minimal Residual Disease ^h							X				X				X ^m		X		
Sample for FoundationOne Mutational Analysis ⁿ	X																		X
Statement of planned allogeneic HCT	X																		
Lumbar Puncture ⁱ	X						X				X				X ^l		X		X
CSF Studies ^j	X						X				X				X ^l		X		X
Day	Screening	1	8	14	15	28	29 +8	36	1	15	29+8	36	1	15	29+8 m	36	Day 38 +8 days of Cycle 5	Q3 MOs	Relapse
Laboratory Procedures																			
CBC with Differential	X	X		X			X	X	X	X	X	X	X	X	X	X	X	X	X
Comprehensive Metabolic Panel (CMP) ^k	X	X		X				X	X	X		X	X	X		X	X		X
Direct Bilirubin	X	X		X				X	X	X		X	X	X		X	X		X
Magnesium	X																		
Phosphate	X																		
Lactate Dehydrogenase	X																		
Uric Acid	X																		
Amylase	X			X				X	X	X		X	X	X		X	X		
Lipase	X			X				X	X	X		X	X	X		X	X		
Coagulation (INR, PT, PTT)	X																		
TSH, Free T4	X													X ^l					
Hepatitis B, C and HIV Serologies	X																		
Serum Pregnancy Test	X																		
Study Assessments																			
Adverse Events	X	X		X		X	X	X	X	X		X	X	X	X	X	X		

Concomitant Medications	X	X		X		X	X	X	X	X		X	X	X	X		X	X	X
-------------------------	---	---	--	---	--	---	---	---	---	---	--	---	---	---	---	--	---	---	---

- a. Blinatumomab 9mcg/day CIV day 1-7
- b. Blinatumomab 28mcg/day CIV
- c. Methotrexate 15mg intrathecal at screening, day 29 +8 days of cycles 1-4, and day 38 +8 days of cycle 5
- d. Vital signs (heart rate and oxygen saturation) to be monitored continuously and full vital signs (temperature, heart rate, blood pressure, respiratory rate, and oxygen saturation) every 4 hours during at least the initial 72 hours of blinatumomab therapy, for 72 hours after all restart or step-up doses, and for at least the initial 72 hours following the first (Cycle 1, Day 15) and third (Cycle 2, Day 15) pembrolizumab doses.
- e. Complete physical exam with full neurologic exam (section 6.1.6)
- f. PET/CT with diagnostic CT chest/abdomen/pelvis (at screening, end of treatment and follow up) or CT chest/abdomen/pelvis if palpable lymphadenopathy or masses at diagnosis
- g. Bone marrow aspirate and biopsy to include standard morphology, flow cytometry, karyotype, and in situ hybridization for t(9;22)(q34;q11.2)[BCR-ABL1]; t(v;11q23)[MLL rearranged]; t(12;21)(p13;q22)[ETV6-RUNX1]; t(1;19)(q23;p13.3)[TCF3-PBX1], institutional standard supercedes
- h. Minimal residual disease by multiparameter flow cytometry per section 7.1.3.
- i. For patients with screening WBC >10,000, LP may be held until WBC ≤10,000. Patient eligible if patient has no signs or symptoms of active CNS involvement at screening.
- j. CSF studies with each lumbar puncture: Cell count with differential, cytology, flow cytometry
- k. Comprehensive metabolic panel (CMP) to include: albumin, alkaline phosphatase, ALT/SGPT, AST/SGOT, BUN, creatinine, electrolytes (sodium, potassium, calcium, chloride, bicarbonate), glucose, and total bilirubin.
- l. TSH and Free T4 to only be collected on Day 1 of Cycle 3 and 5
- m. Only during cycles 3 and 4
- n. See section 6.5.1.1 for details

FLOW CHART- Research Related Samples

Schedule of Events for Research Related Samples														
	Screening	Cycle 1												Cycle 2
Day		1	2	3	8	9	10	14	15	16	17	21	29 +8	Day 29 +8
PD-L1 and PD-L2 lymphoblast Western blotting ^a	X							X					X	
Bone Marrow Correlative Studies (PD-1, PD-L1 Testing), Peripheral blood T-cell subsets ^b	X							X					X	X
Serum Cytokine Assay ^c		X	X	X	X	X	X		X	X	X	X		

a. to be shipped to UCSD per section 6.5.1.2

b. bone marrow aspirate (5 mL) sent to [name] Lab, UCSD per section 6.5.1.3

c. to be drawn prior to, 24 (+/- 2 hours), 48 hours (+/- 2 hours), and 7 days after blinatumomab, blinatumomab dose increase, and first pembrolizumab dose, Sent to UCSD per section 6.5.1.4

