
Pembrolizumab is a potent and highly selective humanized monoclonal antibody (mAb) of the

IgG4/kappa isotype designed to directly block the interaction between PD-1 and its ligands, PD-L1 and PD-L2. Keytruda™ (pembrolizumab) has recently been approved in the United States for the treatment of patients with non-small cell lung cancer or those with unresectable or metastatic melanoma and disease progression following ipilimumab and, if BRAF V600 mutation positive, a BRAF inhibitor.

PD-1 inhibitors including pembrolizumab have promising activity in solid tumors although their activity in acute leukemia is unknown. A Phase Ib/II study of pembrolizumab in relapsed/refractory hematologic malignancies is ongoing. PD-L1, but not PD-L2, is expressed in a subset of ALL primary cells and in most lymphoid leukemia/lymphoma cell lines [11,12]. PD-L1 also tends to be upregulated in the setting of relapsed malignancies including ALL [13,14]. IFN-gamma and TNF-alpha cause upregulation of PD-L1 in acute leukemia [15] which may potentially contribute to resistance to the effects of blinatumomab given the high expression of IFN-gamma, TNF-alpha and other inflammatory cytokines with blinatumomab treatment. Taken together, pembrolizumab holds promise to augment the effect of blinatumomab in patients with relapsed or refractory B-lineage ALL.

Pembrolizumab is generally well tolerated as monotherapy with principal adverse events being rare immune checkpoint blockade-related toxicities. Adverse events in 411 melanoma patients included pneumonitis in 2.9% (0.2% Grade 3), immune-mediated colitis in 1% (0.5% Grade 3), hepatitis in 0.5% (0.2% Grade 4), hypophysitis in 0.5% (0.2% Grade 4), hyperthyroidism in 1.2% (0.2% Grade 3), hypothyroidism in 8.3% (0.2 % Grade 3), type I diabetes mellitus, and immune-mediated nephritis in 0.7% (0.5% Grade 3 or 4). Treatment with prednisone 40 mg or greater per day led to resolution of symptoms in the large majority of patients. Infusion reactions are rare with pembrolizumab but may occur. The effect of pembrolizumab on the developing fetus is unknown.

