3.2 Secondary Endpoints

3.2.1 CR rate as defined above.

3.2.2 Minimal residual disease (MRD) negativity in subjects achieving a CR or CRh will be defined as less than 0.01% residual lymphoblasts by multiparameter flow cytometry.

3.2.3 2-year relapse-free survival (RFS) will be defined as the time from achieving CR or CRh to relapse defined as the reappearance of lymphoblasts in bone marrow or blood at >5% of cells or reappearance of extramedullary disease.

3.2.4 2-year overall survival (OS) will be defined as the time from starting study therapy to death from any cause.

3.2.5 ORR, CR rate, 2-year RFS, and 2-year OS in the Ph/BCR-ABL1-negative and Ph/BCR-ABL1-positive populations separately.

3.2.6 Allogeneic hematopoietic cell transplantation (HCT) rate in transplant-eligible subjects will be defined as the number of patients eligible for allogeneic HCT as determined by the investigator who actually proceed to transplant.

3.2.7 Safety and tolerability of blinatumomab in combination with pembrolizumab will be defined by treatment-emergent Grade 2-5 adverse events (AEs) defined using NCI CTCAE v4.03 toxicity criteria attributable to study therapy.

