Patients achieving a CR/CRh after 2 cycles will complete a total of 5 cycles of blinatumomab and pembrolizumab in the absence of relapse.

Patients not achieving a CR/CRh after 2 cycles of therapy or progressing after Day 15 of Cycle 1 will go off study.

Patients may proceed to allogeneic hematopoietic cell transplantation as consolidation any time after complete remission. Such patients will be censored for survival at time of initiation of conditioning regimen.

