Adverse Event Assessment

Concomitant Medications

Cycles 3 and 4

Day 1

Administration of Blinatumomab 28mcg/d CIV days 1-28

Physical exam, performance status, vital signs, weight

Labs: CBC with differential, CMP (sodium, potassium, chloride, bicarbonate, BUN, creatinine, glucose, calcium, total bilirubin, AST, ALT, alkaline phosphatase), direct bilirubin, amylase, lipase, TSH and T4 (cycles 3 only).

Adverse Event Assessment

Concomitant Medications

Day 15

Administration of Pembrolizumab 200mg IV once

Labs: CBC with differential, CMP (sodium, potassium, chloride, bicarbonate, BUN, creatinine, glucose, calcium, total bilirubin, AST, ALT, alkaline phosphatase), direct bilirubin, amylase and lipase

Adverse Event Assessment

Concomitant Medications

Day 29 + 8 Days

Labs: CBC with differential

Procedures: Bone marrow aspiration and biopsy. Send for standard histology, flow cytometry, cytogenetics (karyotype and *in situ* hybridization for previously documented abnormalities required, additional testing allowed per institutional standard of care) and quantitative PCR for BCR-ABL1 p190 and/or p210 if previously positive.

MRD assessment: 6-color flow cytometry on bone marrow aspirate on at least 0.5×10^6 mononuclear cells when technically possible. MRD assessment to be done on first pull bone marrow aspirate, redirected bone marrow aspirate should be performed as needed for first pull bone marrow aspirate. MRD samples to be sent to University of Washington for analysis (**Section 7.1.3, Appendix C**).

Lumbar puncture with **Methotrexate administration** and CSF studies: Cell count with differential, total protein, random glucose, cytology.

Adverse Event Assessment

Concomitant Medications

Day 36

Administration of Pembrolizumab 200mg IV once

Labs: CBC with differential, CMP (sodium, potassium, chloride, bicarbonate, BUN, creatinine, glucose, calcium, total bilirubin, AST, ALT, alkaline phosphatase), direct bilirubin, amylase and lipase

Adverse Event Assessment

Concomitant Medications

Cycle 5

Day 1

Administration of Blinatumomab 28mcg/d CIV days 1-28

Physical exam, performance status, vital signs, weight

Labs: CBC with differential, CMP (sodium, potassium, chloride, bicarbonate, BUN, creatinine, glucose, calcium, total bilirubin, AST, ALT, alkaline phosphatase), direct bilirubin, amylase, lipase, TSH and T4.

Adverse Event Assessment

Concomitant Medications

Day 15

Administration of Pembrolizumab 200mg IV once

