10.5 Data Analyses Plans

10.5.1 Primary Analysis

Simon's 2-stage for efficacy

We plan a Simon's 2-stage MiniMax design evaluation of the combination of blinatumomab and pembrolizumab in relapsed or refractory B-cell ALL with >50% blasts in the marrow.

We assessed the sample size for studying using overall response rate (CR + CRh). From recent large Phase II study including 189 subjects with relapsed/refractory B-lineage ALL, ORR (CR + CRh) to blinatumomab monotherapy was approximately 29% in patients with >50% lymphoblasts in the bone marrow (Topp et al. 2015). Response rates for PD-1 inhibitors in relapsed or refractory ALL are unknown but given mechanism of action it likely approaches zero.

An absolute increase in the overall response rate of 25 percentage points (i.e. to 54% ORR in patients evaluable for efficacy) or greater will demonstrate sufficient activity to consider the regimen for further study.

To calculate sample sizes for Stage 1 and Stage 2 we used a probability of type I error (α) = 0.05 and a power ($1-\beta$) = 0.80 with $p_0=0.29$ and $p_1=0.54$.

The null hypothesis that the true response rate is 0.29 will be tested against a one-sided alternative. In the first stage, 18 patients evaluable for efficacy will be accrued. If there are 7 or fewer responses in these 18 patients, the study will be stopped. Otherwise, 6 additional patients will be accrued for a total of 24 patients evaluable for efficacy of the combination. The null hypothesis will be rejected if 11 or more responses are observed in 24 evaluable patients. This design yields a type I error rate of 0.05 and power of 0.80 when the true response rate is 0.54. The likelihood of early termination is 0.88, if the null hypothesis is true.

Safety rules

At the time of the Stage 1 efficacy analysis, all patients will be reviewed again for DLTs as defined in Section 5.1.4 occurring at any time during therapy.

A DLT rate exceeding 0.3 will be considered unacceptable. The first 3, 6, 12, and 24 patients will be monitored for DLTs. The first 6 patients will be monitored every other week. The next 6 patients will be monitored monthly. Subsequent patients will be monitored every other month.

k	1	2	3	4
n_k	3	3	6	12

N_k	3	6	12	24
r_k	1	1	3	5

Table: Monitoring design for DLTs. The stage is denoted by k . The number of patients accrued during and up to stage k are denoted by n_k and N_k respectively. The critical value at stage k is denoted by r_k .

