3.3 Endocrine

The following AE terms, if considered \geq Grade 3 or if \geq Grade 2 and require holding/discontinuation/modification of pembrolizumab dosing, are considered ECIs and should be reported to the Sponsor within 24 hours of the event:

- Adrenal insufficiency
- Hyperthyroidism
- Hypophysitis
- Hypopituitarism
- Hypothyroidism
- Thyroid disorder
- Thyroiditis

All attempts should be made to rule out other causes such as brain metastases, sepsis and/or infection. However the AE should be reported regardless of etiology.

Hypophysitis or other symptomatic endocrinopathy other than hypo- or hyperthyroidism

Grade 2-4 events:

- Report as ECI if appropriate
- Hold pembrolizumab
- Rule out infection and sepsis with appropriate cultures and imaging.
- Monitor thyroid function or other hormonal level tests and serum chemistries more frequently until returned to baseline values.
- Pituitary gland imaging should be considered (MRIs with gadolinium and selective cuts of the pituitary can show enlargement or heterogeneity and confirm the diagnosis).
- Treat with prednisone 40 mg p.o. or equivalent per day. When symptoms improve to Grade 1 or less, steroid taper should be started and continued over no less than 4 weeks. Replacement of appropriate hormones may be required as the steroid dose is tapered.
- Permanently discontinue for inability to reduce corticosteroid dose to 10 mg or less of prednisone or equivalent per day within 12 weeks.
- Hypophysitis with clinically significant adrenal insufficiency and hypotension, dehydration, and electrolyte abnormalities (such as hyponatremia and hyperkalemia) constitutes adrenal crisis.
- Consultation with an endocrinologist may be considered.

Hyperthyroidism and Hypothyroidism

Thyroid disorders can occur at any time during treatment. Monitor patients for changes in thyroid function (at the start of treatment, periodically during treatment, and as indicated based on clinical evaluation) and for clinical signs and symptoms of thyroid disorders.

Grade 2 hyperthyroidism, Grade 2-4 hypothyroidism events:

- Report as ECI if appropriate (see Table 1)
- Monitor thyroid function or other hormonal level tests and serum chemistries more frequently until returned to baseline values.
- Thyroid hormone and/or steroid replacement therapy to manage adrenal insufficiency.
- Therapy with pembrolizumab can be continued while treatment for the thyroid disorder is instituted.

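### Patients who leave by the end of Cycle 2 have no scheduled thyroid test after pembrolizumab, so ascertainment of laboratory-detected thyroid events depends on response

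*Combined protocol and SAP*

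**What the plan says.** TSH and free T4 are measured at screening. After that, footnote l to the schedule of events says "TSH and Free T4 to only be collected on Day 1 of Cycle 3 and 5". The visit text in Section 6.2 agrees. The combined entry for Cycles 3 and 4 lists "amylase, lipase, TSH and T4 (cycles 3 only"), Cycle 5 Day 1 lists them again, and Cycles 1 and 2 list none. The laboratory lists for end of treatment (6.2.1), follow-up (6.3) and relapse (6.4) contain no thyroid test.

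Section 5.1.3 gives pembrolizumab on Days 15 and 36 of each 42-day cycle and sets the exit rule: "Patients not achieving a CR/CRh after 2 cycles of therapy or progressing after Day 15 of Cycle 1 will go off study". It adds: "Patients may proceed to allogeneic hematopoietic cell transplantation as consolidation any time after complete remission".

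On safety, Section 3.2.7 states: "Safety and tolerability of blinatumomab in combination with pembrolizumab will be defined by treatment-emergent Grade 2-5 adverse events", limited to events attributable to study therapy. Section 7.2 analyses everyone who received at least one dose of study drug, and Section 10.5.2 reports adverse event rates descriptively. In Section 1.2.2, the melanoma experience includes "hypothyroidism in 8.3% (0.2 % Grade 3"), the highest of the immune toxicity rates quoted there.

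Two passages point towards more testing. Section 8.8.1.2 wants patients assessed for events of clinical interest before every dose, with laboratory results evaluated. Appendix G, Section 3.3, says: "Monitor patients for changes in thyroid function (at the start of treatment, periodically during treatment, and as indicated based on clinical evaluation").

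**The concern.** A site that follows the schedule exactly will look for thyroid dysfunction on treatment only in patients who reach Cycle 3, and those are the responders still on therapy. Patients who leave earlier have had up to four pembrolizumab doses and no scheduled test. In an all-treated rate they count as free of thyroid toxicity unless symptoms led someone to test them. Nothing in Section 10.5.2 separates patients tested and found normal from patients not tested. At stake is how far the reported rate of the protocol's most frequently quoted immune toxicity can be trusted in a trial of at most 24 patients.

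**Working it through.** **Timing.** Study day = 42 × (cycle − 1) + cycle day.

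| Cycle | Day 1 | Pembrolizumab | Scheduled TSH/free T4 |
|---|---|---|---|
| 1 | 1 | 15, 36 | none |
| 2 | 43 | 57, 78 | none |
| 3 | 85 | 99, 120 | 85 |
| 4 | 127 | 141, 162 | none |
| 5 | 169 | 183, 204 | 169 |

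Four doses precede the first scheduled on-treatment test (Day 85). Two doses follow the last (Day 169). The end-of-treatment visit, Cycle 5 Day 38 + 8 days, is study Day 168 + 38 = 206 at the earliest and has no thyroid test.

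**Design figures.** Section 10.5.1 sets the null rate ("The null hypothesis that the true response rate is 0.29 will be tested against a one-sided alternative") and a target of 0.54. The trial stops if 7 or fewer of 18 respond, and rejects the null if 11 or more of 24 respond. With X1 ~ Bin(18, p) and X2 ~ Bin(6, p):

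- Early stopping: P(X1 ≤ 7 | 0.29) = 0.880 (plan: 0.88).
- Type I error: P(X1 ≥ 8 and X1 + X2 ≥ 11 | 0.29) = 0.0499 (plan: 0.05).
- Power: the same probability at 0.54 = 0.801 (plan: 0.80).

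The plan's figures reproduce, so 0.29 and 0.54 are the rates on which the design rests.

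**Patients with no scheduled test after pembrolizumab, from non-response alone.**

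- Target rate: 1 − 0.54 = 46%; 24 × 0.46 = 11.0 patients.
- Null rate: 1 − 0.29 = 71%. The trial then stops at 18 with probability 0.88, so the relevant count is 18 × 0.71 = 12.8, about 13 of 18.
- At the stopping boundary (7 of 18 respond): 11 of 18 = 61%. Fewer responders means more untested.
- At the smallest success (11 of 24 respond): 13 of 24 = 54%.
- Ceiling at 24: enrolment continues only with at least 8 responders among the first 18, so non-responders cannot exceed (18 − 8) + 6 = 16.

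Responders who go to transplant before Day 85 add to these counts. The documents give no rate for them.

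**The case against.** The strongest reply is that untested on schedule is not the same as unobserved. Section 8.1 records adverse events in every patient to 30 days after treatment ends. Section 8.8.1.2 requires patients to be asked about immune-related symptoms before each dose, with further testing when an event is suspected, and Appendix G allows thyroid testing when clinically indicated. This stands: symptomatic events should be found in early leavers too. It does not cover a laboratory abnormality that nobody measured. Appendix G gives no dates and describes its own management recommendations as guidelines, whereas footnote l is explicit and restrictive.

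Several stronger readings are tempting, and the documents do not support them.

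- *Early leavers are never tested.* They have no scheduled test; indicated testing remains open to them.
- *Seventeen of 24 go untested* (24 × 0.71). This many non-responders cannot occur, because the stage 1 rule caps them at 16 of 24.
- *The reported rate will be 2.8% to 5.1% instead of 9.5%.* This adds 8.3% hypothyroidism and 1.2% hyperthyroidism and multiplies by 0.29 and 0.54. It assumes that events are found only by scheduled tests and that incidence is equal after at most four doses and after up to ten. The melanoma rates are also not limited to attributable Grade 2-5 events. The only grade-specific thyroid figures in Section 1.2.2 are 0.2% Grade 3 for each disorder.
- *Dose-limiting toxicities will be missed.* The monitoring window contains no thyroid test, but most laboratory-only thyroid findings would not qualify. Grade 3-4 laboratory abnormalities count only if they warrant interrupting pembrolizumab or permanently stopping blinatumomab. Section 5.7.1 leaves pembrolizumab unchanged for hypothyroidism of any grade and for Grade 2 hyperthyroidism.
- *Planned comparisons by response or time on treatment are confounded.* No such thyroid comparison is planned.

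**Conclusion.** The point holds as a gap in ascertainment. Followed as written, the plan schedules no thyroid test after pembrolizumab for anyone who leaves by the end of Cycle 2, and none after the Cycle 5 doses. The 46% to 71% range is derived here and is not a figure in the documents. It rests on the two design response rates and on the exit rule being applied as stated, and early transplants would raise it.

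The consequence is conditional. Thyroid events found mainly by laboratory testing may be under-ascertained, more so the fewer patients respond. The shortfall in attributable Grade 2-5 events cannot be sized from the documents, because they give neither a Grade 2-5 thyroid rate nor the share of such events that would come to light through symptoms. For symptomatic events it may be nil. The primary analysis is unaffected. The matter still merits action because the gap is certain even though its effect is not, and the remedy is small.

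**What to change.** 1. Reconcile the restriction in footnote l with Section 8.8.1.2 (assessment and laboratory review before each dose) and Appendix G, Section 3.3 (periodic thyroid monitoring). The aim is for TSH/free T4 to be run on blood already drawn after pembrolizumab in Cycles 1-2 and at end of treatment. Which visits to use is for the sponsor to choose. The table, footnote l and Sections 6.2 and 6.2.1 should then agree. An end-of-treatment sample from Day 206 would fall as little as 2 days after the Day 204 dose, so it would say more about the earlier doses than the last.

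2. In Section 10.5.2, keep the all-treated thyroid event rate and report beside it the number of patients with at least one thyroid test after pembrolizumab and the rate among them. The tested-only rate should not replace the all-treated one. On the current schedule it would describe mainly responders, plus patients tested because they had symptoms, which exchanges one bias for another.

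The cost is a few extra routine assays per patient on existing draws, consistent schedule wording and one sentence in Section 10.5.2. The downside is some additional subclinical findings to report. The second change needs no new data collection.
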